15.3 Definition of Dose-limiting Toxicity (DLT)

A Dose Limiting Toxicity is defined as any event that meets the DLT criteria listed in this section, unless unequivocally due to underlying malignancy or an extraneous cause.

Any participants receiving AZD4573 beyond the dose escalation/DLT-assessment period will be monitored for safety using the same DLT criteria used during the DLT-assessment period.

The SRC will make a recommendation to stop or continue recruitment after review of the data from each cohort (see Section [18.6](#)).

The DLT-assessment period applicable in Part A of this module is normally 5 weeks (DLT observation will continue throughout the study for Part A and Part B). Any participant who does not complete the DLT-assessment period in Part A may be replaced, with the exception of a participant who experiences a DLT; these participants will not be replaced.

Additional participants enrolled at a previously-cleared dose level to provide supplemental safety, efficacy, PK, and pharmacodynamics data will not be replaced or evaluated for DLT in support of dose-escalation decisions. However, these additional participants will be included in the determination of MTD/RP2D at the end of the dose-escalation process.

Any AE that meets the DLT criteria in the opinion of the principal Investigator should be reported to the Medical Monitor within 24 hours of knowledge of the event.

A DLT will be defined as the occurrence of any of the following, unless unequivocally due to underlying malignancy or an extraneous cause:

DLT criteria (CTCAE version 5.0):

- Any Grade ≥ 3 non-haematological toxicity except:
 - Grade 3 nausea, vomiting, or diarrhoea despite premedication that respond to medical management (eg, improve by 1 or more severity grade within 72 hours of onset of toxicity, or 96 hours [-2/+12 hours] from the start of dose, whichever is the sooner).
 - Grade ≥ 3 serum lipase and/or amylase that return to initial eligibility criteria within 72 hours of onset of toxicity or 96 hours (-2/+12 hours) post start of dose, whichever is the sooner. Grade ≥ 3 serum lipase and/or amylase that do not return to meet initial eligibility criteria within 72 hours of onset of toxicity or 96 hours (-2/+12 hours) post start of dose, whichever is the sooner, will be considered a DLT.

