- A delay in dosing of more than approximately 7 consecutive days (\pm 2 days), in other words, more than 1 missed dose, due to a dose-related toxicity occurring during the 5-week DLT-assessment period (toxicity that is clearly and directly related to the primary disease or to another aetiology is excluded from this definition).

Isolated elevations of transaminases:

- Grade 3 elevations ($\geq 5 \times$ ULN) in ALT or AST, without concomitant elevation in total bilirubin $> 2 \times$ ULN, that do not return to Grade 1 within 7 days from start of dosing.
- Grade 4 elevations in ALT ($\geq 20 \times$ ULN) of any duration irrespective of total bilirubin.
- Grade 4 elevations in AST ($\geq 20 \times$ ULN) without concomitant elevation in ALT $\geq 20 \times$ ULN or total bilirubin $\geq 2 \times$ ULN that do not return to Grade 1 within 7 days from start of dosing.

Elevations in transaminases with concomitant elevation of bilirubin (Potential Hy's Law [PHL]):

- Elevations in ALT or AST $\geq 3 \times$ ULN with concomitant elevation in total bilirubin $\geq 2 \times$ ULN where bilirubin does not return to meet initial eligibility criteria within 72 hours of onset or 96 hours of start of dosing (-2/+12 hours) whichever is the sooner, and/or ALT or AST do not return to meet initial eligibility criteria within 7 days post start of dose.
- Elevations in ALT or AST $\geq 3 \times$ ULN with concomitant elevation in total bilirubin $\geq 2 \times$ ULN and INR $> 1.5 \times$ ULN (or $> 1.5 \times$ baseline, if elevated at baseline) of any duration.
- Elevations in ALT or AST $\geq 3 \times$ ULN with concomitant elevation in total bilirubin $\geq 2 \times$ ULN of any duration if associated with symptoms or signs of liver impairment (eg, appearance of fatigue, nausea, vomiting, right upper quadrant pain or tenderness, fever, rash, and/or eosinophilia $> 5\%$).

Any of the following haematological toxicities:

- CTCAE Grade 4 neutrophil count decrease lasting > 7 days, despite growth factor support.
- Grade ≥ 3 febrile neutropenia (absolute neutrophil count [ANC] $< 1.0 \times 10^9/L$, fever $> 100.9^{\circ}\text{F}$ [or $> 38.3^{\circ}\text{C}$]) of any duration despite supportive care.
- CTCAE Grade 4 thrombocytopenia lasting more than 7 days or Grade ≥ 3 thrombocytopenia, of any duration, associated with \geq Grade 2 bleeding.

- CTCAE Grade 4 anaemia despite transfusion.

Any Tumour Lysis Syndrome meeting the following criteria:

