- Grade ≥ 3 clinical TLS ([Appendix F](#)) that occurs despite protocol-recommended management will be considered a DLT.
- Laboratory TLS ([Appendix F](#)) will be considered a DLT if the metabolic abnormalities do not resolve within 5 days despite protocol-recommended management.

Note: All DLT events of TLS should be graded according to the Howard modification of the Cairo-Bishop criteria as part of TLS monitoring (Section [17.1.5](#) and [Appendix F](#)), while CTCAE grade should be applied on AE/SAE reports.

The definition of DLT excludes:

- 1 Grade 3 fatigue for ≤ 7 days after onset.
- 2 Isolated laboratory changes of any grade without clinical sequelae or clinical significance, with the exception of transaminase and bilirubin abnormalities described above.
- 3 Isolated changes in GGT (ie, with no corresponding elevation in AST, ALT, ALP, Total bilirubin or INR, and no symptoms suggestive of hepatic injury) will not be classified as a DLT.

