Grade 4^c Isolated AST elevation $\geq 20 \times$ ULN without concomitant elevation in ALT $\geq 20 \times$ ULN or TBL $\geq 2 \times$ ULN	1st occurrence If recovered to Grade ≤ 1 or baseline level within 7 days of the start of the infusion allow rechallenge at same dose level 2nd occurrence If recovered to Grade ≤ 1 or baseline level within 7 days of the start of the infusion allow rechallenge with 1 dose level reduction 3rd occurrence Discontinue AZD4573	Withhold or continue acalabrutinib (at Investigator discretion, after discussion with the Medical Monitor). To prevent disease progression, monitor disease parameters closely. Monitor ALT, AST, ALP, and bilirubin at least 1x per week. After 7 days if hepatic enzymes appear to be improving and acalabrutinib was withheld, restart acalabrutinib at current dose level at the 1st occurrence and with 1 level dose reduction at the 2nd occurrence . Discontinue acalabrutinib at the 3rd occurrence .
Concurrent elevations in ALT, AST, or bilirubin (Please also refer to Appendix E for actions to be taken in the event of PHL)		
ALT or AST $\geq 3 \times$ ULN with TBL $\geq 2 \times$ ULN (Potential Hy's Law) AND INR $\geq 1.5 \times$ ULN (or $\geq 1.5 \times$ baseline if elevated at baseline) of any duration	Discontinue AZD4573.	Discontinue acalabrutinib.
ALT or AST $\geq 3 \times$ ULN with the appearance of fatigue, nausea, vomiting, right upper quadrant pain or tenderness, fever, rash, and/or eosinophilia $> 5\%$	Discontinue AZD4573.	Discontinue acalabrutinib.
ALT or AST $\geq 3 \times$ ULN and TBL $\geq 2 \times$ ULN where TBL does not return to baseline level within 96 hours (-2/+12 hours) from start of dose and/or AST or ALT do not return to baseline level within 7 days from start of dose	Discontinue AZD4573.	Discontinue acalabrutinib.

Event ^a	Action	
	AZD4573	Acalabrutinib
Grade 3 elevation ($\geq 5 \times$ ULN) in ALT or AST with TBL elevation above baseline level or ULN, but $< 2 \times$ ULN that do not return to baseline level within 7 days	Discontinue AZD4573.	Discontinue acalabrutinib.

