ALT and AST $\geq 3 \times$ ULN with concomitant TBL $\geq 2 \times$ ULN, NO increase in INR $\geq 1.5 \times$ ULN (or $1.5 \times$ baseline), and NO fatigue, nausea, vomiting, right upper quadrant pain or tenderness, fever, rash, and/or eosinophilia $> 5\%$	If recovered to Grade ≤ 1 or baseline level within 96 (-2/+12) hours, rechallenge at same dose level ^c	Withhold acalabrutinib until recovered. Once recovered, restart acalabrutinib at same dose.

^a Adverse reactions are graded using National Cancer Institute CTCAE version 5.0. All grades refer to CTCAE grading except for TLS, which uses the Howard modification of Cairo-Bishop criteria (Howard et al 2011).

^b Elevations in ALT or AST are considered isolated if bilirubin remains below Grade 1, and elevations in bilirubin are considered isolated if ALT and AST remain below Grade 1.

^c Participants who are considered for rechallenge in the event of Grade 4 transaminase increases or PHL must discuss possible risk of hepatotoxicity with the treating physician, who will document this discussion and participant agreement for continued treatment in the medical records.

Note: Adequate supportive therapy as per institutional guidelines should be given for all toxicities.

Abbreviations: ALP = alkaline phosphatase; ALT = alanine aminotransferase; AST = aspartate aminotransferase; CTCAE = Common Terminology Criteria for Adverse Events; INR = international normalised ratio; PHL = Potential Hy's Law; TBL = total bilirubin; ULN = upper limit of normal.

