17.1.10.9 Liver Chemistry Test Abnormalities and the Risk of Liver Injury

Transaminase elevations are an important potential risk for patients treated with acalabrutinib, and an important identified risk for participants treated with AZD4573. Reactivation of hepatitis B infection has been observed in patients treated with acalabrutinib. Participants should be made aware of the risk of possible overlapping toxicities of transaminase elevations while receiving both drugs. Evidence of abnormal liver chemistry should be monitored as per the protocol guidelines. Increased levels of AST, ALT, or serum bilirubin should trigger an investigation of the cause, which may include viral infection or disease progression with liver infiltration. The Investigator should consider whether the abnormal liver chemistry meets the criteria for expedited reporting.

Bilirubin increase with transaminase increase is included as an important identified risk for AZD4573. Biochemical changes of increased transaminases with concomitant increase in bilirubin fulfilling criteria for Hy's law have been observed in participants treated with AZD4573. These events resolve rapidly and have to date not been associated with any adverse clinical sequelae or lasting liver damage. Upon rechallenge with AZD4573, there is no consistent pattern of recurrence, nor is there any consistent increase in severity of the events. As such, while the events follow the biochemical definition of Hy's law, the clinical pattern is rapidly self-limiting and does not seem to predict any lasting liver damage.

Participants who experience elevated ALT/AST $\geq 3 \times$ ULN and/or elevated total bilirubin $\geq 2 \times$ ULN after AZD4573 dosing must be closely monitored with repeated liver chemistry tests (INR, fibrinogen, D-dimer [where available at institution], ALP, ALT, AST, GLDH (if a GLDH test cannot be performed at the site or locally, LDH will be sufficient), CPK, total bilirubin, direct bilirubin, indirect bilirubin) are required at least every 48 hours (-2/+12 hours) after the start of the infusion and until resolution of the event. **CCI**

██████████ will also be collected (see Section [17.9.6](#)).

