If bilirubin fails to resolve within 96 hours (-2/+12 hours) or transaminases fail to resolve within 7 days, or if the event is associated with significant clotting abnormality or clinical symptoms of liver disease, study treatment must be permanently discontinued (the participant remains on study for the 30-day SFU and long-term follow-up [LTFU] visits), and the event must be immediately communicated to AstraZeneca.

For guidance on treating liver toxicity, please refer to [Table 14](#) of this protocol.

During the course of the study the Investigator will remain vigilant for increases in liver biochemistry. The Investigator is responsible for determining whether a participant meets PHL criteria at any point during the study.

Please refer to [Appendix E](#) for the process to be followed to identify and appropriately report cases of PHL. It is not intended to be a comprehensive guide to the management of elevated liver biochemistries.

The Investigator will participate, together with the Medical Monitor, in review and assessment of PHL events to agree whether HL criteria are met. HL criteria are met if there is no alternative explanation for the elevations in liver biochemistry.

The Investigator is responsible for recording data pertaining to PHL/HL cases and for reporting AEs and SAEs according to the outcome of the review and assessment in line with standard safety reporting processes.

Regarding the hepatic toxicity events encountered to date with AZD4573, it has been observed that while the biochemical changes of increased transaminase with concomitant elevation in bilirubin seen in some participants could be classified as HL by its strict definition, they do not follow a pattern that is consistent with true HL predictive of hepatic injury, and are therefore 'PHL' cases. The events are rapidly resolved and to date have not led to any clinical sequelae or lasting hepatic injury. Repeated dosing with AZD4573 following these events has demonstrated that there is no consistent pattern of recurrence and no consistent increase in severity of the events if they do recur.

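### Section 15.3 both counts and does not count, as a DLT, a recovering asymptomatic Potential Hy's Law event with a Grade ≥3 component

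*Protocol*

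**What the plan says.** Section 15.3 of the protocol (Module 1) lists the DLT criteria as alternatives: one is enough.

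- **General item.** Any Grade ≥ "3 non-haematological toxicity except" two groups: Grade 3 nausea, vomiting or diarrhoea that responds to management, and Grade ≥3 lipase/amylase that recovers in time. ALT, AST and bilirubin are not among the exceptions.
- **Isolated transaminase items.** Grade 3 ALT/AST without bilirubin above 2 × ULN, and Grade 4 AST without ALT at 20 × ULN or bilirubin at 2 × ULN, are DLTs if they are rises "that do not return to Grade 1 within 7 days from start of dosing". Grade 4 ALT is a DLT at any duration.
- **PHL items**, under a separate heading. ALT or AST ≥3 × ULN with bilirubin ≥2 × ULN is a DLT "where bilirubin does not return to meet initial eligibility criteria within 72 hours of onset or 96 hours of start of dosing", or where ALT/AST have not recovered by 7 days. With an INR rise, or with symptoms or signs of liver impairment, it is a DLT at any duration.
- **Exclusion 2.** Isolated laboratory changes without clinical sequelae or significance are not DLTs, "with the exception of transaminase and bilirubin abnormalities described above".

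Elsewhere, footnote b of Table 14 (Section 15.12) says: "Elevations in ALT or AST are considered isolated if bilirubin remains below Grade 1". Section 8.2.6 requires PHL cases to be reported as SAEs on grounds of medical significance. The last row of Table 14 allows rechallenge at the same dose after a PHL event that recovers without INR rise or symptoms.

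**The concern.** The general item and the PHL item give opposite answers for the same event, and no clause says which prevails. If the general item applies as written, the recovery windows have no effect on any Grade ≥3 liver rise.

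The event class is relevant to this drug. Section 17.1.10.9 reports combined transaminase and bilirubin rises meeting the biochemical Hy's law definition with AZD4573, and adds: "These events resolve rapidly and have to date not been associated with any adverse clinical sequelae or lasting liver damage". It does not give their grades.

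DLTs are a Part A primary endpoint (Table 7), the MTD is defined by the DLT rate (Section 15.4), and backfilled participants count towards MTD/RP2D (Section 15.3). Investigators judge in the first instance whether an event meets the criteria, so two sites could score the same event differently.

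**Working it through.** **1. Event by event.** Grade limits are those printed in Table 14: ALT/AST Grade 2 is above 3 to 5 × ULN and Grade 3 is above 5 to 20; bilirubin Grade 2 is above 1.5 to 3 × ULN and Grade 3 is above 3 to 10. Rows are asymptomatic with no INR rise unless stated.

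| Event | General item | Specific liver item | Exclusion 2 | Status |
|---|---|---|---|---|
| PHL, Grade 2 on each test, recovers | no | no | not needed | not a DLT |
| PHL, ALT/AST >5 × or bilirubin >3 × ULN, ALT <20 × ULN, recovers | yes | no | not clearly applicable | **unresolved** |
| Isolated Grade 3 ALT/AST, recovers within 7 days | yes | no | probably excludes it | probably not a DLT |
| Isolated Grade 4 AST, recovers within 7 days | yes | no | probably excludes it | probably not a DLT |
| Grade 4 ALT | yes | yes | carved out | DLT |
| PHL with INR rise or symptoms | yes, if Grade ≥3 | yes | carved out | DLT |

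**2. Exclusion 2.** The phrase "with the exception of transaminase and bilirubin abnormalities described above" can mean abnormalities that meet the criteria above, or transaminase and bilirubin abnormalities as a class. On the first and likelier meaning, a recovering isolated enzyme rise is excluded and the conflict goes. A recovering PHL event must still qualify as isolated and not clinically significant. Section 15.3 lists PHL apart from isolated elevations, footnote b requires bilirubin below Grade 1, and Section 8.2.6 treats PHL as medically significant. So exclusion 2 does not clearly reach it.

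**3. Isolated bilirubin.** It has no liver item of its own. On the class meaning it stays under the general item; on the other it could be excluded. Any rewording must not drop it by accident.

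**4. The decision table itself is sound.** Table 11 was recomputed with a Beta(1,1) prior (assumed; the protocol passages cited here state none). The score for each interval is its posterior probability divided by its length, the stay interval is 0.25 to 0.35, and the dose is unsafe if P(p > 0.30) ≥ 0.95. All cells for n = 3 to 9 match. For example, 0/3 gives Beta(1,4): the stay interval scores (0.75⁴ − 0.65⁴)/0.10 = (0.3164 − 0.1785)/0.10 = 1.38, and 0 to 0.05 scores (1 − 0.95⁴)/0.05 = 0.1855/0.05 = 3.71, hence escalate. The question is only what is fed into the table.

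**5. Sensitivity to one event.** Using raw proportions against the Section 15.4 band of 25% to 35%, one reclassified event crosses a band edge here:

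- n = 6: 1 to 2 (16.7% to 33.3%) and 2 to 3 (33.3% to 50.0%)
- n = 9: 2 to 3 (22.2% to 33.3%) and 3 to 4 (33.3% to 44.4%)
- n = 21, with backfill: 5 to 6 (23.8% to 28.6%) and 7 to 8 (33.3% to 38.1%)

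That is 2 of the 6, 9 and 21 possible one-event steps respectively. These figures hold for any added DLT and say nothing about how often this conflict arose.

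**The case against.** The strongest reply is that the intent is evident. If the general item swallowed every Grade ≥3 liver rise, the recovery windows would be pointless, so the headed liver blocks must govern. Section 13.3 records that, in the first-in-human study, reversible asymptomatic isolated Grade 4 enzyme rises were judged not to be DLTs and that protocol was amended. Table 14 allows same-dose rechallenge after recovering PHL. Footnote b serves dose modification, and Section 15.3's own isolated heading tolerates bilirubin up to 2 × ULN. The carve-out also names bilirubin, and the only raised-bilirubin criteria above it are the PHL ones, which suggests that PHL was thought to fall within exclusion 2.

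Much of this stands. It disposes of the isolated transaminase case and shows what the sponsor probably meant for PHL. It does not supply a rule: the criteria are alternatives, no precedence is stated, and where a recovery exception to the general item was wanted (lipase/amylase) it was written into that item. PHL also has its own heading and is called medically significant in Section 8.2.6. Section 13.3 speaks of isolated rises, not PHL.

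**Conclusion.** The conflict is real but narrow. The firm case is a recovering, asymptomatic PHL event with no INR rise, a Grade ≥3 component and ALT below 20 × ULN. It is worth fixing because it sits in the rule for a primary endpoint and the cure is short.

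A reader might infer three stronger things that the document does not support:

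- **That every recovering Grade ≥3 liver rise is in dispute.** The likelier reading of exclusion 2 settles isolated Grade 3 ALT/AST and Grade 4 AST, and PHL at Grade 2 on each test never meets the general item.
- **That dose escalation will be misdirected.** Section 4.1 says recruitment has stopped, Table 11 only guides the SRC, and the RP2D rests on aggregate safety data (Section 15.5). What remains is the reported Part A DLT counts and the MTD/RP2D statement.
- **That the first-in-human experience gives a rate.** The 2 of 6 participants at 12 mg in Section 13.3 had isolated AST rises on monotherapy. Section 17.1.10.9 describes PHL-type rises without grades. The frequency in Module 1 is unknown.

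The band calculation assumes raw proportions and shows sensitivity, not likelihood.

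**What to change.** 1. Add to the first item's exceptions: *ALT/AST elevations, and concomitant ALT/AST and bilirubin elevations (PHL), without symptoms or signs of liver impairment and without INR > 1.5 × ULN (or > 1.5 × baseline if elevated at baseline), which are DLTs only if they meet the transaminase or PHL criteria below.* Grade ≥3 rises with symptoms or an INR rise remain DLTs. This agrees with Table 14, which stops both drugs for ALT or AST ≥3 × ULN "with the appearance of fatigue, nausea, vomiting, right upper quadrant pain or tenderness, fever, rash, and/or eosinophilia" above 5%, and with Section 17.1.10.9, where, if an event is "associated with significant clotting abnormality or clinical symptoms of liver disease, study treatment must be permanently discontinued".
2. Reword the carve-out in exclusion 2 to: *transaminase and PHL abnormalities meeting the criteria above, and isolated Grade ≥3 bilirubin.* Isolated Grade ≥3 bilirubin then stays under the general item. Add no new bilirubin thresholds; those would be a clinical choice made after enrolment closed, not a correction.
3. When reporting Part A DLTs, list any event whose status differs from that used at the SRC.

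The cost is two edits and a short listing. The data are already required by Section 17.1.6: chemistry at 24 hours in Cycles 1 to 3, then for qualifying rises repeats at 48 and 96 hours and every 48 hours until resolution. For a rise first seen at 24 hours, 24 + 72 = 96, so both bilirubin limits fall on the 96-hour sample. The drawback is that reported counts may differ from those the SRC saw, which the listing makes visible.
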